#### **5.4.3 Rescue Medications & Supportive Care**

Participants should receive appropriate supportive care measures as deemed necessary by the treating investigator. Suggested supportive care measures for the management of AEs with potential immunologic etiology are outlined along with the dose modification guidelines in Section 5.2.2, [Table 3]. Where appropriate, these guidelines include the use of oral or IV treatment with corticosteroids, as well as additional anti-inflammatory agents if symptoms do not improve with administration of corticosteroids. Note that several courses of steroid tapering may be necessary as symptoms may worsen when the steroid dose is decreased. For each disorder, attempts should be made to rule out other causes such as metastatic disease or bacterial or viral infection, which might require additional supportive care. The treatment guidelines are intended to be applied when the Investigator determines the events to be related to pembrolizumab.

Note: If after the evaluation of the event, it is determined not to be related to pembrolizumab, the Investigator does not need to follow the treatment guidance. Refer to [Table 3] in Section 5.2.2 for guidelines regarding dose modification and supportive care.

It may be necessary to perform conditional procedures such as bronchoscopy, endoscopy, or skin photography as part of evaluation of the event.

#### **5.5 Participant Withdrawal/Discontinuation Criteria**

Participants may discontinue study treatment at any time for any reason or be dropped from the study treatment at the discretion of the investigator should any untoward effect occur. In addition, a participant may be discontinued from study treatment by the investigator or the Sponsor if study treatment is inappropriate, the trial plan is violated, or for administrative

and/or other safety reasons. Specific details regarding procedures to be performed at study treatment discontinuation are provided in Section 7.1.4 – Other Procedures.

A participant must be discontinued from study treatment but continue to be monitored in the study for any of the following reasons:

- The participant or participant's legally acceptable representative requests to discontinue study treatment
- Confirmed radiographic disease progression outlined in Section 7.1.2.6
- Unacceptable adverse experiences as described in Section 5.2.2.
- The participant has a medical condition or personal circumstance which, in the opinion of the investigator and/or sponsor, placed the participant at unnecessary risk from continued administration of study treatment.
- The participant has a confirmed positive serum pregnancy test
- Recurrent Grade 2 pneumonitis
- The participant is lost to follow-up
- Completion of 15 treatments (approximately 1 year) with pembrolizumab

Note: The number of treatments is calculated starting with the first dose. Participants who stop the combination or pembrolizumab after receiving 15 doses may be eligible for retreatment if they progress after stopping study treatment. Participants may be retreated in the Second Course Phase (Retreatment) for up to an additional 17 cycles (approximately 1 year).

- Administrative reasons

## 5.6 Clinical Criteria for Early Trial Termination

Early trial termination will be the result of the criteria specified below:

1. Quality or quantity of data recording is inaccurate or incomplete
2. Poor adherence to protocol and regulatory requirements
3. Incidence or severity of adverse drug reaction in this or other studies indicates a potential health hazard to participants
4. Plans to modify or discontinue the development of the study drug

In the event of Merck decision to no longer supply study drug, ample notification will be provided so that appropriate adjustments to participant treatment can be made.

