#### **4.6.2.2 Safety Endpoints**

- Severe (grade  $\geq 3$ ) adverse events, scored using CTCAE v 4.03.
  - It will be important to characterize the toxicity profile of sequential pembrolizumab and radiotherapy for locally advanced NSCLC, as this is a novel treatment approach.
- Pneumonitis (grade  $\geq 2$ ).
  - It will be important to characterize the rate of pneumonitis, which may occur because of radiotherapy or immunotherapy, for study subjects.
- Patient-reported treatment-related toxicity, scored using PRO-CTCAE.
  - See Section 4.5
- Unplanned hospitalization.
  - Many patients treated with radiotherapy or chemoradiotherapy for locally advanced NSCLC are hospitalized due to treatment toxicity. It will be important to characterize the hospitalization rate for patients treated with pembrolizumab and radiotherapy for locally advanced NSCLC.
- Daily step counts, measured using wearable fitness trackers.
  - See Section 4.4

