**Table 3 Dose modification and toxicity management guidelines for immune-related AEs associated with pembrolizumab**

General instructions:				
Immune-related AEs	Toxicity grade or conditions (CTCAEv4.0)	Action taken to pembrolizumab	irAE management with corticosteroid and/or other therapies	Monitor and follow-up
Pneumonitis	Grade 2	Withhold	
 
Administer corticosteroids (initial dose of 1-2 mg/kg prednisone or equivalent) followed by taper
 
	
 
Monitor participants for signs and symptoms of pneumonitis
 
Evaluate participants with suspected pneumonitis with radiographic imaging and initiate corticosteroid treatment
 
Add prophylactic antibiotics for opportunistic infections
 

	Grade 3 or 4, or recurrent Grade 2	Permanently discontinue		
Diarrhea / Colitis	Grade 2 or 3	Withhold	
 
Administer corticosteroids (initial dose of 1-2 mg/kg prednisone or equivalent) followed by taper
 
	
 
Monitor participants for signs and symptoms of enterocolitis (ie, diarrhea, abdominal pain, blood or mucus in stool with or without fever) and of bowel perforation (ie, peritoneal signs and ileus).
 
Participants with <math>\geq</math> Grade 2 diarrhea suspecting colitis should consider GI consultation and performing endoscopy to rule out colitis.
 
Participants with diarrhea/colitis should be advised to drink liberal quantities of clear fluids. If sufficient oral fluid intake is not feasible, fluid and electrolytes should be substituted via IV infusion.
 

	Grade 4	Permanently discontinue		

AST / ALT elevation or Increased bilirubin	Grade 2	Withhold	
 
Administer corticosteroids (initial dose of 0.5- 1 mg/kg prednisone or equivalent) followed by taper
 
	
 
Monitor with liver function tests (consider weekly or more frequently until liver enzyme value returned to baseline or is stable)
 

	Grade 3 or 4	Permanently discontinue	
 
Administer corticosteroids (initial dose of 1-2 mg/kg prednisone or equivalent) followed by taper
 
	

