For the purpose of data collection, all untoward events that occur after informed consent through 90 days after the last dose of study drug must be recorded on the subject’s CRF by the investigational site. This requirement includes AEs from unscheduled as well as scheduled visits. The investigator is responsible for ensuring that all AEs and SAEs that are observed or reported during the study are recorded on appropriate CRFs and reported in accordance with protocol instructions. The study period during which all AEs must be

reported begins after informed consent is obtained and study treatment is initiated and ends 90 days after last administration of study treatment, or at the time of initiation of another anti-cancer therapy, whichever occurs first. AEs and SAEs that are observed or reported prior to initiation of study treatment should be recorded on appropriate CRFs if they are associated with protocol-mandated interventions (e.g., invasive procedures such as biopsies).

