## 7.2 Assessing and Recording Adverse Events

An adverse event is defined as any untoward medical occurrence in a patient or clinical investigation participant administered a pharmaceutical product and which does not necessarily have to have a causal relationship with this treatment. An adverse event can therefore be any unfavorable and unintended sign (including an abnormal laboratory finding, for example), symptom, or disease temporally associated with the use of a medicinal product or protocol-specified procedure, whether or not considered related to the medicinal product or protocol-specified procedure. Any worsening (i.e., any clinically significant adverse change in frequency and/or intensity) of a preexisting condition that is temporally associated with the use of the Merck's product, is also an adverse event.

Merck product includes any pharmaceutical product, biological product, device, diagnostic agent or protocol-specified procedure, whether investigational (including placebo or active comparator medication) or marketed, manufactured by, licensed by, provided by or distributed by Merck for human use.

Adverse events may occur during the course of the use of Merck product in clinical trials, or as prescribed in clinical practice, from overdose (whether accidental or intentional), from abuse and from withdrawal.

All AEs, SAEs and other reportable safety events that occur after the consent form is signed but before treatment allocation/randomization must be reported by the investigator if the participant is receiving placebo run-in or other run-in treatment, if the event causes the participant to be excluded from the study, or is the result of a protocol-specified intervention, including but not limited to washout or discontinuation of usual therapy, diet, or a procedure.

- All AEs from the time of treatment allocation/randomization through 30 days following cessation of study treatment must be reported by the investigator.
- All AEs meeting serious criteria, from the time of treatment allocation/randomization through 90 days following cessation of study treatment, or 30 days following cessation of study treatment if the participant initiates new anticancer therapy, whichever is earlier must be reported by the investigator.

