**SAE reports and any other relevant safety information are to be forwarded to the Merck Global Safety [contact]**

**SAE reports and any other relevant safety information are to be forwarded to Principal Investigator ([name]., [[contact]](mailto:[contact])) as well as the study sponsor's Data Safety Monitoring Committee ([[contact]](mailto:[contact])).**

A copy of all 15 Day Reports and Annual Progress Reports is submitted as required by FDA, European Union (EU), Pharmaceutical and Medical Devices agency (PMDA) or other local regulators. Investigators will cross reference this submission according to local regulations to the Merck Investigational Compound Number (IND, CSA, etc.) at the time of submission. Additionally, investigators will submit a copy of these reports to Merck & Co., Inc. (Attn: Worldwide Product Safety; [contact]) at the time of submission to FDA.

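### The only trial-level toxicity criterion for the PembroRT cohort is qualitative: no observed event count obliges an accrual pause or a committee review

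*Combined protocol and SAP*

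**What the plan says.** Section 5.6 is firm in form: "Early trial termination will be the result of the criteria specified below". Item 3 of its list is the toxicity criterion: "Incidence or severity of adverse drug reaction in this or other studies indicates a potential health hazard to participants". The other three items concern data quality, adherence and the drug's development. The section provides for termination only, with no intermediate pause or review.

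Oversight is described in Section 7.2.3.1. Serious adverse events go to the sponsor within 24 hours, whether or not related to the drug. In addition, "SAE reports and any other relevant safety information are to be forwarded to Principal Investigator" "as well as the study sponsor's Data Safety Monitoring Committee". That is the committee's only appearance in the public text. No meeting schedule, trigger or authority is given.

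The remaining toxicity rules are for individual patients. For pneumonitis, Table 3 permanently discontinues pembrolizumab at "Grade 3 or 4, or recurrent Grade 2". Table 4, Section 5.5 and the esophagitis hold in Section 5.2.3 work in the same way. Section 8.2 reports adverse events as counts and percentages with exploratory cohort comparisons. Neither 8.1 nor 8.2 plans an interim safety look.

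On pneumonitis, Section 4.6.2.2 says: "It will be important to characterize the rate of pneumonitis, which may occur because of radiotherapy or immunotherapy, for study subjects".

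**The concern.** The sponsor calls the regimen a novel approach. It gives a PD-1 antibody before and after accelerated thoracic radiotherapy, and both can cause pneumonitis. Three features make unaided judgement a weak trigger here.

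- Item 3 speaks of drug reactions, and Section 5.4.3 applies the Table 3 guidance when the investigator judges an event related to pembrolizumab. Pneumonitis attributed to radiation can fall outside both.
- Patients come from Montefiore and three further sites (Section 5.7), so no single site sees the running total.
- The study is open-label and hopes to show fewer severe events and no significant rise in pneumonitis (Section 3.2, objectives 5 and 6).

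Without a pre-set count, the point at which enrolment pauses has no known error rates. At stake is how many of the 25 PembroRT patients start treatment before someone is obliged to look at the accumulated events.

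**Working it through.** **1. The plan's own figures.** The plan gives no toxicity rate or boundary to reproduce. Its one power figure (81%, Section 8.1) concerns PFS. With hazards −ln 0.40 = 0.916 and −ln 0.65 = 0.431 per year, uniform 18-month accrual, n = 25, two-sided 5%, and an assumed 12 months of follow-up after accrual, the standard one-sample log-rank test has 80.6% power. Nothing below depends on that figure.

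**2. What the current text obliges.** For X ~ Binomial(25, p), P(X ≥ 8) is 10.9% at p = 20%, 48.8% at 30% and 84.6% at 40%. In the text, neither 8 events nor any other number carries a required action.

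**3. An illustrative boundary.**
- From the documents: 25 patients and 18 months of accrual (Section 8.1).
- Assumed: an acceptable grade ≥3 pneumonitis rate p0 = 10%, and accrual uniform over the period (random or evenly spaced).
- Window: 9 weeks of induction + 4 weeks of radiotherapy + about 13 weeks (90 days) = 26 weeks, about 6 months. Onset is assumed uniform over months 0–6 or 2.1–6.
- Denominator: patients who have had a first pembrolizumab dose. Each event counts at onset.

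The boundary at n patients is the smallest x ≥ 2 with P(X ≥ x | n, p0) ≤ c, where c = 0.052. For example, P(X ≥ 3 | 8, 0.10) = 0.038, so 3 events suffice at n = 8. P(X ≥ 3 | 9, 0.10) = 0.053 exceeds c, so 4 are needed at n = 9. The result:

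| Patients started | Pause for review at |
|---|---|
| 2–3 | ≥2 events |
| 4–8 | ≥3 |
| 9–14 | ≥4 |
| 15–20 | ≥5 |
| 21–25 | ≥6 |

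**4. How it behaves.** Simulation with 20,000 trials per cell; ranges span the four accrual and onset settings.

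| True rate | Reached at any time | Reached while accrual is open | Mean enrolled if every trigger closes accrual |
|---|---|---|---|
| 10% | 4–5% | 2–3.5% | 24.6–24.8 |
| 20% | 40–42% | 22–30% | 22.1–23.2 |
| 30% | 82–83% | 58–68% | 17.7–19.8 |
| 40% | 97–98% | 85–91% | 13.7–16.2 |

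The last column is a limiting case. The proposed rule pauses accrual; if the committee reopens it, enrolment returns to 25 over a longer period.

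**5. Sensitivity.**
- Acceptable rate: with p0 of 5%, 15% or 20% (c = 0.066, 0.046, 0.040), the boundary is reached at a true 30% in 97%, 50–53% or 20–24% of trials.
- Accrual (p0 = 10%): over 12 months the false-trigger rate is 3.3–3.8%; over 36 months it is 5.7–6.5%.
- Denominator: the same p0 = 10% boundary gives 15–20% false triggers over patients with an event or a completed window, and 20–26% over completed windows only. The rule must therefore define its denominator.

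**The case against.** The strongest reply is that oversight exists and the missing number may sit elsewhere. Item 3 is mandatory in form. Serious adverse events reach the sponsor within 24 hours. Table 7 describes grade 3 partly by hospitalization being indicated, so many grade ≥3 pneumonitis cases would already be serious events that go to the committee. Section 10.0 has only its heading in the public text, and the committee appears to be a standing body that may have its own charter. All of this stands, and it makes the point a recommended improvement rather than an error. A reader might infer that the trial lacks safety oversight or cannot stop for toxicity; the documents do not support that.

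A second reply is that the gain is modest unless toxicity is high. At twice the assumed acceptable rate, the boundary is reached during open accrual in only 22–30% of trials. That also stands, and no document supports a 30–40% rate. It is likewise tempting to read the mean-enrolment column as patients spared. That holds only if the committee closes accrual at each trigger, which the rule does not require.

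Third, the collection windows differ. Section 5.7 says "all untoward events that occur after informed consent through 90 days after the last dose of study drug must be recorded", although its reporting period ends sooner if new anti-cancer therapy starts. Section 7.2 says "All AEs from the time of treatment allocation/randomization through 30 days following cessation of study treatment must be reported by the investigator". One might infer that severe pneumonitis would go uncollected. The documents do not show that: maintenance pembrolizumab runs to about one year, and serious events are reported to 90 days (30 if new therapy starts). The gap mainly concerns non-serious events after early discontinuation, so it is a side issue that the rule's wording can settle.

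**Conclusion.** The point holds in a limited form. In the public text, Section 5.6 item 3 is the only trial-level toxicity criterion for the PembroRT cohort. It is qualitative, and no count obliges a pause or a review. What is missing is a numeric trigger, not monitoring.

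This is a design choice that the sponsor should reconsider; no stated result of the plan is wrong. The size rests on assumed toxicity rates, onset patterns and uniform accrual. Under these, a simple rule would oblige a review in most trials with a true rate of 30% or more, at a false-trigger rate of about one in twenty or less at 10%. Confidence is medium, because a charter or the unseen Section 10.0 may already hold a rule.

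**What to change.** Keep item 3. If a committee charter already holds a numeric rule, cite it in Section 5.6. Otherwise add, in substance:

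> PembroRT accrual pauses for Data Safety Monitoring Committee review when the number of patients with grade ≥3 pneumonitis of any cause reaches the boundary for the number of PembroRT patients who have received a first pembrolizumab dose. Events count at onset, from the first pembrolizumab dose to 90 days after the end of radiotherapy or, if radiotherapy is not given, to 90 days after the last pembrolizumab dose. Each patient counts once and stays in the denominator. After the 25th patient the boundary triggers review only.

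Put the boundary table and its operating characteristics in Section 8. The sponsor should choose the acceptable rate; 10% is only an illustration. The grade ≥2 endpoint of Section 4.6.2.2 with a higher rate is an alternative.

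State that grade ≥3 pneumonitis is reported to the sponsor within 24 hours, like a serious adverse event, and forwarded to the committee. State also that it is collected for the whole window above, regardless of the 30-day limit in Section 7.2 or the start of new therapy.

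Cost: one paragraph, one table, one reporting clarification, and prompt reporting of a few non-serious events. The planned 25 patients and the PFS test stay as they are unless the committee closes accrual. A pause could lengthen the 18-month accrual period. Under the stated assumptions, the chance of a needless review at the acceptable rate is 4–5%.

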## 5.7 Study Registration and Data Management

Most study subjects will be enrolled by the study sponsors at Montefiore Medical Center. This study will also be activated at three additional subsites (Rogel Cancer Center-University of Michigan, New York University Langone Health and Henry Ford Cancer Institution). The following procedures will be performed for registration of each study subject:

- (subsites only) Notify sponsor when a patient is in screening. If an ICF is signed, a copy of the ICF will be sent to the sponsor.
- (all sites) Complete screening procedures and generate a signed eligibility checklist
- (subsites only) Send a copy of the signed eligibility checklist to the sponsor.
- (sponsor only) Enroll study subject with CPDMU and in Velos. All subjects will be registered through the Clinical Trials Office at Montefiore Medical Center ([contact], Monday through Friday 9:00am – 5:00pm Eastern Standard Time). The “On Study Form” and the completed Informed Consent Form will be emailed to the clinical trials office at Montefiore Medical Center, ([contact]) at the time of registration and prior to patient treatment initiation. At the time of registration, all eligibility criteria must be checked. A signed eligibility checklist will be stored for each subject.
- (all sites) Complete local study subject registration processes.

Study data will be warehoused by the lead investigators at Montefiore Medical Center and the Albert Einstein College of Medicine. Data for study subjects who are treated at other institutions will be recorded on electronic case report forms (CRF) in a deidentified manner and transmitted to the Montefiore/Einstein investigators. Data for subjects from institutions other than Montefiore will be recorded in Velos in a de-identified manner following our institutional standard operating procedure, where subjects are given a de-identified medical record number (eg: “NYU-01-001”) and an approximate date of birth is entered. Local investigators will be responsible for maintaining a log linking study subject identification numbers to patient identities. Local investigators must complete local subject registration processes and maintain accurate documentation (source data) that supports the information entered in the CRF.

For the purpose of data collection, all untoward events that occur after informed consent through 90 days after the last dose of study drug must be recorded on the subject’s CRF by the investigational site. This requirement includes AEs from unscheduled as well as scheduled visits. The investigator is responsible for ensuring that all AEs and SAEs that are observed or reported during the study are recorded on appropriate CRFs and reported in accordance with protocol instructions. The study period during which all AEs must be

reported begins after informed consent is obtained and study treatment is initiated and ends 90 days after last administration of study treatment, or at the time of initiation of another anti-cancer therapy, whichever occurs first. AEs and SAEs that are observed or reported prior to initiation of study treatment should be recorded on appropriate CRFs if they are associated with protocol-mandated interventions (e.g., invasive procedures such as biopsies).

## 6.0 TRIAL FLOW CHART

PD-L1 ≥ 50%: PembroRT	Eval Week:	Induction Pembrolizumab									Radiotherapy							Maintenance Pembrolizumab													
		1	2	3	4	5	6	7	8	9	10	11	12	13	14	15	16	17	18	21	24	27	30	33	36	39	42	45	48	51	
History, Physical, Toxicity Assessment	X	X			X			X			X	X	X	X	X	X	X	X	X	X	X	X	X	X	X	X	X	X	X		
PRO-CTCAE Assessment	X	X			X			X			X	X	X	X	X	X	X	X	X	X	X	X	X	X	X	X	X	X	X		
PET/CT	X																														
CT C/A																															
Biopsy, Tumor PD-L1 Testing	X																														
Serum Correlative Studies	X																														
Pembrolizumab																															
Dose-Painted Radiotherapy																															
PD-L1 < 50%: ChemoRT	Eval Week:	Chemoradiotherapy										Optional Adjuvant Therapy, Observation																			
		1	2	3	4	5	6	7	8	9	10	11	12	13	14	15	16	17	18	21	24	27	30	33	36	39	42	45	48	51	
History, Physical, Toxicity Assessment	X	X	X	X	X	X	X	X	X	X	X+																				
PRO-CTCAE Assessment	X	X		X		X		X		X	X+																				
PET/CT	X																														
CT C/A																															
Biopsy, Tumor PD-L1 Testing	X																														
Serum Correlative Studies	X																														
Carboplatin/Paclitaxel																															
Radiotherapy																															
		XXXXX	XXXXX	XXXXX	XXXXX	(XXXXX)	(XXXXX)	(XXXXX)	(XXXXX)	(XXXXX)		(X*)							(X*)												

( ) - Optional

^ - May be replaced by PET/CT

\* - Every 3 weeks, starting 4-6 weeks after completion of radiotherapy

+ - May be performed one week before or after the protocol-specified timepoint

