**Hypothesis:** We hypothesize that sequential pembrolizumab and radiotherapy for locally advanced NSCLC not significantly increase rates of pneumonitis compared to standard concurrent chemoradiotherapy.

(7) **Objective:** To demonstrate, within the limitations of a nonrandomized study, that sequential pembrolizumab and radiotherapy for locally advanced NSCLC reduces patient-reported treatment-related toxicities compared to standard concurrent chemoradiotherapy.

**Hypothesis:** We hypothesize that sequential pembrolizumab and radiotherapy for locally advanced NSCLC reduces patient-reported treatment-related toxicities compared to standard concurrent chemoradiotherapy.

(8) **Objective:** To demonstrate, within the limitations of a nonrandomized study, that sequential pembrolizumab and radiotherapy for locally advanced NSCLC preserves physical function compared to standard concurrent chemoradiotherapy.

**Hypothesis:** We hypothesize that sequential pembrolizumab and radiotherapy for locally advanced NSCLC preserves physical function, as measured by daily step counts, compared to standard concurrent chemoradiotherapy.

(9) **Objective:** To demonstrate, within the limitations of a nonrandomized study, that sequential pembrolizumab and radiotherapy for locally advanced NSCLC reduces hospitalization rates compared to standard concurrent chemoradiotherapy.

**Hypothesis:** We hypothesize that sequential pembrolizumab and radiotherapy for locally advanced NSCLC reduces hospitalization rates compared to standard concurrent chemoradiotherapy.

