### 8.2 Statistical Analysis Plan – Secondary Endpoints

Time-to-event outcomes (overall survival, freedom from distant metastasis, freedom from intrathoracic progression, freedom from hospitalization) will be analyzed using the Kaplan-Meier method, from which rates at various time points and corresponding 95% confidence intervals will be estimated. Exploratory comparisons for time-to-event outcomes between the PembroRT and ChemoRT cohorts will be performed using log-rank tests. Univariate and

multivariable Cox regression models will be used to evaluate associations between time-to-event outcomes and clinical covariates, including study cohort.

Rates of radiographic responses and disease progression during induction pembrolizumab for subjects in the PembroRT cohort will be described using counts and percentages. Logistic regression models will be used to evaluate potential predictors of response or progression (e.g.: PD-L1 TPS).

Hospitalization rates and adverse event rates, scored using CTCAE as well as PRO-CTCAE, will be presented as counts and percentages. Exploratory comparisons between the PembroRT cohort and the ChemoRT cohort will be performed using chi-square or Fisher Exact testing, as appropriate.

Daily step counts throughout the study period will be presented using descriptive statistics and will be analyzed using a generalized linear mixed-model for repeated measures.

Rates of circulating tumor DNA clearance will be presented as counts and percentages, and predictors of circulating tumor DNA clearance will be explored using chi-square or Fisher exact testing, as appropriate. Exploratory analyses will be performed to evaluate PD-L1 expression, expression of alternative immune checkpoint molecules (e.g., HHLA2, B7x, and B7-H3), baseline tumor mutational burden, and markers of immune activation (e.g., expansion of T4/T8 subsets, myeloid derived suppressor cell levels, expansion of T-cell repertoire) as predictors of PFS and overall survival.

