## Appendix 5: PRO-CTCAE Assessment Tool

### NCI PRO-CTCAE™ ITEMS

#### Item Library Version 1.0

As individuals go through treatment for their cancer they sometimes experience different symptoms and side effects. For each question, please check or mark an  in the one box that best describes your experiences over the past 7 days...

1.	In the last 7 days, what was the SEVERITY of your DIFFICULTY SWALLOWING at its WORST?				
 None  Mild  Moderate  Severe  Very severe					

2.	In the last 7 days, what was the SEVERITY of your DECREASED APPETITE at its WORST?				
 None  Mild  Moderate  Severe  Very severe					
In the last 7 days, how much did DECREASED APPETITE INTERFERE with your usual or daily activities?					
 Not at all  A little bit  Somewhat  Quite a bit  Very much					

3.	In the last 7 days, how OFTEN did you have NAUSEA?				
 Never  Rarely  Occasionally  Frequently  Almost constantly					
In the last 7 days, what was the SEVERITY of your NAUSEA at its WORST?					
 None  Mild  Moderate  Severe  Very severe					

4.	In the last 7 days, what was the SEVERITY of your SHORTNESS OF BREATH at its WORST?				
 None  Mild  Moderate  Severe  Very severe					
In the last 7 days, how much did your SHORTNESS OF BREATH INTERFERE with your usual or daily activities?					
 Not at all  A little bit  Somewhat  Quite a bit  Very much					

5.	In the last 7 days, what was the SEVERITY of your COUGH at its WORST?				
 None  Mild  Moderate  Severe  Very severe					
In the last 7 days, how much did COUGH INTERFERE with your usual or daily activities?					

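### PRO-CTCAE is scheduled at different frequencies in the two cohorts and section 8.2 sets no common window, so the exploratory objective 7 comparison partly reflects how often each cohort was asked

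*Combined protocol and SAP*

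**What the plan says.** **Objective.** Secondary objective 7 (section 3.2) aims to show, within the stated limits of a non-randomized study, that PembroRT "reduces patient-reported treatment-related toxicities compared to standard concurrent chemoradiotherapy".

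**Schedule (section 6.0; blank cells are lost in the quotes).**
- The PembroRT row begins "PRO-CTCAE Assessment X X X X X X X X X X X X X". Set against the week header, these marks are evaluation, weeks 1, 4 and 7, then every week from 10, where the radiotherapy heading begins, to 18. The row then continues every three weeks.
- The ChemoRT row is "PRO-CTCAE Assessment X X X X X X X": evaluation, weeks 1, 3, 5, 7 and 9, and a last mark with a plus sign. The footnote to that sign reads "May be performed one week before or after the protocol-specified timepoint".
- The ChemoRT clinician row is "History, Physical, Toxicity Assessment X X X X X X X X X X X", which is weekly over weeks 1-9. The two-week gap therefore belongs to the patient-reported row.

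**Instrument (Appendix 5).** Patients choose the answer that "best describes your experiences over the past 7 days".

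**Analysis (section 8.2).** The plan says that "adverse event rates, scored using CTCAE as well as PRO-CTCAE, will be presented as counts and percentages", with exploratory between-cohort chi-square or Fisher exact tests. It gives no assessment window, no severity threshold, no rule for reducing repeated forms to one result per patient, and no adjustment for the number of forms.

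**The concern.** With a 7-day recall, a form every two weeks leaves alternate weeks unobserved, while a weekly form leaves none. A chi-square or Fisher test needs one yes/no per patient. When a patient has several forms, the obvious yes/no is whether any form reached the chosen level. That proportion rises with the number of forms even when true toxicity is identical.

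Two things are at stake. A real reduction in patient-reported toxicity could be hidden, or an apparent difference produced, by the schedule alone. And because the sign of the distortion changes with the window, leaving the window open in an open-label trial lets the result turn on a choice made after the data have been seen.

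**Working it through.** **1. Cohort sizes (section 8.1).** PembroRT 25. With 40% of patients at PD-L1 of at least 50%, ChemoRT = 25 × 0.60/0.40 = 37.5, about 38, total 63. This reproduces the plan. The plan gives no power or sample size for objective 7.

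**2. Scheduled forms by window, from section 6.0 as printed.**
- First nine weeks from the start of radiotherapy: PembroRT weeks 10-18 = 9; ChemoRT weeks 1, 3, 5, 7, 9 = 5.
- Study weeks 1-9: PembroRT weeks 1, 4, 7 = 3; ChemoRT = 5.

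**3. Formula.** Let q be the chance that a form reaches the chosen level, m the number of forms and ρ the within-patient correlation.
- Independent forms: P(ever) = 1 − (1 − q)^m.
- Correlated forms (beta-binomial): a = q(1 − ρ)/ρ, b = (1 − q)(1 − ρ)/ρ, and P(ever) = 1 − ∏ (b + i)/(a + b + i) for i = 0 to m − 1.

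The documents give neither q nor ρ. I assume q = 10% in both cohorts, so true risk is equal, and ρ = 0, 0.3 or 0.6. For example, 1 − 0.9^9 = 61.3% and 1 − 0.9^5 = 41.0%. At ρ = 0.3, a = 0.233 and b = 2.1.

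| Forms, PembroRT v ChemoRT | ρ = 0 | ρ = 0.3 | ρ = 0.6 |
|---|---|---|---|
| 9 v 5 (from radiotherapy start) | 61.3% v 41.0% | 34.6% v 27.1% | 21.5% v 18.5% |
| 8 v 5 (if one mark is misplaced) | 57.0% v 41.0% | 33.1% v 27.1% | 20.9% v 18.5% |
| 3 v 5 (study weeks 1-9) | 27.1% v 41.0% | 20.8% v 27.1% | 15.8% v 18.5% |

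The 8 v 5 row is there because the printed PembroRT row stops at week 48 although the header runs to 51. Of the 20 columns from week 10 onward, 19 are marked, so a one-cell shift could leave one of weeks 10-18 blank.

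**4. Effect on the test.** Exact enumeration of the two-sided Fisher test at an assumed 0.05 level, 25 v 38 patients, using the rates above:
- Equal true risk, 9 v 5 forms: PembroRT is falsely found worse in 31%, 8% and 4% of trials (ρ = 0, 0.3, 0.6). With equal numbers of forms the figure is about 2%.
- True halving of the per-form risk (10% v 20%), 9 v 5 forms: observed rates are 61% v 67%, 35% v 48% and 22% v 35%. The chance of a significant result favouring PembroRT is 6%, 15% and 14%.
- The same halving with 5 v 5 forms: rates are 41% v 67%, 27% v 48% and 18% v 35%, and that chance is 50%, 33% and 22%.

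**The case against.** **The plan never says ever reported.** This is right. Section 8.2 would also fit a test at each timepoint or in each phase, and such a test would be less exposed. A reader might infer that the plan commits to a biased measure. The text supports less: the measure is undefined, and its most natural reading is sensitive to the schedule.

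**The direction is not fixed.** A reader might infer that the schedule simply works against PembroRT. It does so when counting starts at radiotherapy. Over study weeks 1-9 the counts reverse to 3 v 5 and the distortion favours PembroRT.

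**Symptoms last.** Section 5.2.3 says acute esophagitis may persist for 4-6 weeks, so a form every two weeks would usually meet such an episode, though it could miss the worst week. It cannot be claimed that a severe episode in an unasked week is lost. Lasting symptoms correspond to the higher correlations, where the 9 v 5 gap falls to about 3 percentage points.

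**Whole-course totals.** The chart as printed shows 22 v 6 forms after evaluation, and a reader might take from this a very large contrast. The table has visibly lost cells: several rows are blank or displaced, and later ChemoRT marks may be missing. That count should not be used.

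**Matching changes the question.** Objective 7 concerns the whole sequential strategy. A test limited to forms from the start of radiotherapy leaves out induction and most maintenance toxicity, which could flatter PembroRT. Phases also need not line up. The sequential boost option for PembroRT is 17 + 3 = 20 fractions, about 4 weeks at five a week; ChemoRT may run 20-37 fractions, about 4 to 7.4 weeks. Both points stand, and the fix has to allow for them.

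**The comparison is exploratory and non-randomized.** Sections 4.6 and 8.2 say so. This limits the priority, but it does not excuse an avoidable measurement difference added to the confounding.

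**Conclusion.** The concern holds in a limited form. As printed, PembroRT patients are asked about weekly and ChemoRT patients every two weeks from the start of radiotherapy, and section 8.2 does nothing to put the two on the same footing. If each patient is classed by any report at a given level, the objective 7 comparison partly measures how often patients were asked.

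At an assumed equal 10% risk per form and 9 v 5 forms, the spurious gap is about 20 percentage points with independent forms, 7.5 at correlation 0.3 and 3 at 0.6. Over study weeks 1-9 it has the opposite sign. These sizes rest on the assumed risk and correlation, a constant risk across forms, and the flow chart as extracted. Losing one PembroRT mark (8 v 5) does not change the conclusion.

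The documents do not support a claim of fixed bias against PembroRT, nor any figure for the whole course. Priority is modest, because the comparison is exploratory and non-randomized and the primary PFS endpoint is unaffected.

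**What to change.** Add to section 8.2, before the cohorts are compared:

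1. For the between-cohort PRO-CTCAE test, use the same number and spacing of forms counted from the start of radiotherapy. For example, take every second PembroRT form (weeks 10, 12, 14, 16, 18) against ChemoRT weeks 1, 3, 5, 7, 9, after checking these weeks against the original flow chart.
2. Define the per-patient result as the worst score per item over those forms, and state the threshold used for the percentages.
3. Label the result as patient-reported toxicity from the start of radiotherapy, not of the whole strategy.
4. Report PembroRT induction and maintenance PRO-CTCAE rates beside it, without a between-cohort test, so that pembrolizumab toxicity stays visible.

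**Cost.** Wording only; every form is already scheduled. The extra PembroRT forms do not enter the test. The matched weeks may fall in different treatment phases because radiotherapy length differs between cohorts, and this should be stated with the result.
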